APPENDIX I  
STUDY FLOW CHART

Procedure/Test	Visit #1 (Baseline)	Visit #2 (Study Days 5-7)	Visit #3 (Study Days 2-4 after therapy)	Visit #4 (Study Days 21-28 after therapy)	Early Withdrawal
Medical History	X				
Physical Exam	X	X	X	X	X
Chest X-ray	X		X	X*	X*
Culture & Gram stain	X		X	X*	X*
Blood Samples	X		X		X
Pregnancy Test	X				
Pharmacokinetics	X	X			
Urinalysis	X		X		X
Signs and Symptoms	X	X	X	X	X
Adverse Events		X	X	X	X
Clinical Response			X	X	X

\* Repeat only if positive at Visit #3 (Study Days 2-4 After Completion of Therapy)

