## **DESCRIPTION OF STUDY**

This is a multicenter, prospective, randomized, Phase III study to evaluate the safety and efficacy of Drug A compared with cefuroxime axetil in the treatment of community-acquired pneumonia in adults.

Investigators will collectively enroll approximately 450 outpatient subjects with community-acquired pneumonia to ensure clinically evaluable data from 400 subjects. The study will be terminated when 200 clinically evaluable subjects per treatment group have been prospectively enrolled. The study may be amended if necessary to ensure enrollment of sufficient numbers of subjects with infections due to critical pathogens. The data will be pooled across investigators for safety and efficacy analyses. A subject is eligible for study entry if the infection was acquired in a community setting.

Subjects who meet all the inclusion criteria and exhibit none of the exclusion criteria may be enrolled. A Potential Subject Roster, which will document the initials of each patient considered for study entry, the date of assessment, severity of diagnosis and the reasons for not enrolling any potential study subject, will be maintained at each site. As subjects qualify for the study, subject numbers will be assigned in strict sequential order at each site. Subjects will receive one of two treatment regimens according to a computer-generated randomization schedule prepared by the CCRP Pharmaceuticals, Inc. and kept at the individual investigational sites. This randomization schedule will provide for equal numbers of subjects in the two regimens. The random study group assignment will be provided for each subject in individually sealed envelopes. As a qualified subject enters the study, the next available randomization envelope in the sequence will be opened to reveal the appropriate therapy regimen. The following two regimens will be used:

- 1. Drug A 500 mg PO q12h**
- 2. Cefuroxime axetil 500 mg PO q12h**

Total therapy duration will be 7 to 14 days, as clinically indicated. A minimum of five days of therapy will be required for analysis of microbiologic response, unless subjects have failed clinically and have taken sufficient drug to be considered evaluable within this time. If, in the opinion of the investigator, a subject requires more than 14 days of therapy (e.g., *Legionella pneumophila*, slowly resolving pneumonia, etc.) the medical monitor should be contacted.

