**C. Visit #3 - Post-Therapy Evaluation (Study Days 2-4 After Completion of Therapy)**

The investigator should assess the subject's overall clinical progress and assess adverse events.

Clinical response will be determined by comparing a subject's post-therapy signs and symptoms to those observed on admission as well as by comparing post-therapy chest x-ray findings with those on admission, as follows:

Cure:	Resolution of signs and symptoms associated with active infection along with resolution of chest x-ray findings
Improved:	Incomplete resolution of signs, symptoms, and chest x-ray findings
Failure:	No response to therapy
Unable to Evaluate:	Due to the administration of non-study antimicrobials, I insufficient course of therapy, subject not returning for post-therapy evaluation, etc.

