**The following will be performed:**

1. Physical examination, including vital signs
2. Evaluate subject for signs and symptoms of pneumonia
3. Culture and Gram stain of respiratory secretions
4. Obtain venous blood samples and urine studies listed for baseline visit
5. Repeat chest x-ray
6. Assess adverse events
7. Instruct subjects to contact the investigator immediately if they experience a return of symptoms
8. Urinalysis

9. Evaluate clinical response

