**D. Visit #4 - Post-Study Evaluation (Study Days 21-28 After Completion of Therapy)**

1. Physical exam, including vital signs
2. Evaluate subject for signs and symptoms of pneumonia
3. Culture and Gram stain of respiratory secretions, if still positive at Visit #3 (Study Days 2-4 After Completion of Therapy)
4. Repeat chest x-ray, if pneumonia not resolved at Visit #3 (Study Days 2-4 After Completion of Therapy)
5. Clinical response will be assessed by comparing the subject's pre-study signs and symptoms (including pre-study chest x-ray findings) to those observed post-therapy:
  - Cure - resolution of signs and symptoms associated with active infection, along with resolution of chest x-ray findings
  - Improved - continued incomplete resolution of signs and symptoms with no deterioration or relapse during the follow-up period
  - Failure - no response to therapy
  - Relapse - resolution or improvement of signs and symptoms at the post-therapy evaluation with reappearance or deterioration of signs and symptoms of infection.
  - Unable to Evaluate - due to the administration of non-study antimicrobials, subject not returning for post-study evaluation, etc.
6. Assess adverse events

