**E. Early Withdrawal from the Study**

In the event a subject withdraws from therapy prematurely, the same procedures as in Visit #3 (Study Days 2-4 After Completion of Therapy) should be performed at the time of study withdrawal. The reason for early therapy withdrawal should be documented on the appropriate case record form. Schedule follow-up visit, if appropriate.

To date approximately 150 subjects have been given Drug A. The most frequently reported side effects are outlined in the table below:

Possible Risk/Side Effect	How often has it	How serious is it?
---------------------------	------------------	--------------------

	occurred	
Nausea	It is expected to occur	Can be easily treated
Diarrhea	It is expected to occur	Can be easily treated
Vomiting	It is uncommon	Can be treated
Changes in certain levels in your blood chemistry	It is uncommon	Very Serious
Dizziness	It occasionally occurs	Can be treated
Restlessness	It occasionally occurs	Can be treated
Tremors	It occasionally occurs	Can be treated
Headache	It is expected to occur	Can be easily treated
Rash	It occasionally occurs	Can be treated

**Allergic reaction to any antibiotic in the past should be documented or noted by the investigator or the study coordinator because the study subject may have an allergic reaction to antibiotics used in this study. These allergic reactions may be life threatening.**

The risks of drawing blood from a vein includes discomfort at the site of the needle stick, possible bruising and swelling around the site of the needle stick, rarely an infection, and uncommonly feeling faint from the procedure.”

The risks of Drug A and Cefuroxime axetil to an unborn child are unknown. Therefore, if the study subject is capable of giving birth to or fathering a child, he/she should use adequate birth control measures while on the study. These measures may include abstinence, oral contraceptives (birth control pills), IUD, diaphragm, Norplant, approved hormone injections, condoms, or documentation of medical sterilization.

This research study involves exposure to radiation from chest x-rays. The amount of radiation exposure from this procedure(s) is equivalent to a uniform whole body exposure of 10 millirems. This is equivalent to 5 % of the amount of natural environmental radiation the average person receives annually. The risk from radiation exposure of this magnitude is too small to be detected in this population.

Severe and Unanticipated Adverse Events:

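### Appendix I ties the early-withdrawal chest x-ray and culture to a Visit #3 result that subjects stopping on therapy do not have, contradicting Section V.E

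*Protocol*

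**What the plan says.** Section V.E opens with the case it covers, "In the event a subject withdraws from therapy prematurely", and then directs that "the same procedures as in Visit #3 (Study Days 2-4 After Completion of Therapy) should be performed at the time of study withdrawal". The Visit #3 list in Section V.C includes "Culture and Gram stain of respiratory secretions" and "Repeat chest x-ray", neither with a condition.

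Appendix I also has an Early Withdrawal column. Blood samples, urinalysis, signs and symptoms, and clinical response each carry a plain X there. Chest x-ray and culture carry X*, and the footnote reads "Repeat only if positive at Visit #3 (Study Days 2-4 After Completion of Therapy".

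Two other places bear on the consequence. The Description of Study, repeated under Randomization in Section 2.2, sets a five-day minimum of therapy for the microbiologic analysis, "unless subjects have failed clinically and have taken sufficient drug to be considered evaluable within this time". Section V.C defines Cure as "Resolution of signs and symptoms associated with active infection along with resolution of chest x-ray findings", while Failure is simply a lack of response and names no film.

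**The concern.** The footnote presupposes a Visit #3 that a subject who stops on therapy has not had. Read literally, its condition is never satisfied for such a subject, so the chart calls for neither test, while Section V.E calls for both. Section V introduces the chart as the diagram of the study procedures, and 20 to 25 sites are expected, so different sites could act on different texts.

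At stake is outcome information that cannot be collected later. Eradication is judged from respiratory cultures, and the protocol deliberately lets some early clinical failures count in that analysis. A site following the chart would not take the post-baseline culture from them. The clinical rating is also due at withdrawal and is meant to compare the follow-up film with the admission film.

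**Working it through.** No figure of the plan is in dispute, so the check sets the provisions side by side.

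| Test | V.C, Visit #3 | V.D, Visit #4 | V.E, early withdrawal | Appendix I, Early Withdrawal |
|---|---|---|---|---|
| Culture and Gram stain | Unconditional | Only if still positive at Visit #3 | As Visit #3, so unconditional | X*, only if positive at Visit #3 |
| Chest x-ray | Unconditional | Only if pneumonia unresolved at Visit #3 | As Visit #3, so unconditional | X*, only if positive at Visit #3 |
| Blood samples, urinalysis | Unconditional | Not listed | As Visit #3, so unconditional | X |
| Clinical response | Unconditional | Unconditional | As Visit #3, so unconditional | X |

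1. *Can the footnote's condition be met?* Visit #3 is timed two to four days after therapy is completed. A subject who withdraws during therapy has not reached it, so there is no result to be positive. The condition can be met only by someone who leaves between Visits #3 and #4.

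2. *Where does the condition belong?* Section V.D sets it for Visit #4, for example "Culture and Gram stain of respiratory secretions, if still positive at Visit #3". No other section sets it. In the Early Withdrawal column the blood, urine and clinical-response rows agree with Section V.E; only the two starred rows depart from it. That pattern suggests an asterisk carried over from the Visit #4 column.

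3. *Which endpoint depends on the missing tests?* The Description of Study says that the microbiological data come from cultures of respiratory secretions, so that endpoint depends on the culture directly. The clinical rating uses the film in its general comparison and in the wording of Cure and Improved, but not in the wording of Failure.

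4. *Can the effect be sized?* Not from the protocol. The inputs needed are the share of failures that withdraw on therapy, the share of sites that follow the chart rather than Section V.E, and the response rates. None is given; Section VIII states alpha 0.05, power 85% and 200 per group without rates or a difference. The nearest figure is in Section 1: Drug A was stopped prematurely in 3.5% of earlier courses. Applied to half of the 450 planned subjects, 0.035 × 225 = 7.9, about 8 in the Drug A group; if the same rate held in both groups, 0.035 × 450 = 15.75, about 16 in all. These counts suggest how many subjects might reach an early-withdrawal assessment under that assumption. They do not say how many are failures or how many would miss a test.

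**The case against.** The strongest reply is that Section V.E is an explicit sentence written for this very situation, and nothing ranks the chart above it. A site that reads Section V.E obtains both tests. One could also read the footnote as applying only where a Visit #3 has taken place, or read the column as meant for subjects who leave after Visit #3. These readings are possible, but the chart states none of them, and the last would leave it with no rule for the withdrawals that Section V.E describes. The contradiction therefore stands, and what follows from it is a risk and not a certainty.

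A reader might go further and infer that early failures will drop out of both analyses, inflating both rates and costing the trial power. The documents do not support that, for these reasons:

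- Failure can be rated without a film. The chart still requires the physical examination, signs and symptoms, and clinical response at withdrawal.
- The examples given for Unable to Evaluate are non-study antimicrobials, an insufficient course and not returning. A missing film is not among them, though the list is open-ended. Subjects in those categories could be unevaluable even with both tests done, and correcting the chart would not bring them back.
- Nothing in the protocol says that on-therapy withdrawals are mainly failures, and the handling of a missing culture may be set out in a statistical analysis plan that is not at hand.
- Enrolment continues until 200 clinically evaluable subjects per group are reached, so clinically unevaluable subjects are replaced. A power calculation that lets the group size shrink would misstate the effect. Replacement would not undo a selective loss, but its size remains unknown.

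**Conclusion.** The point holds as an internal contradiction with a possible effect on outcome data. Appendix I, as written, would have a site omit the chest x-ray and culture for a subject withdrawing on therapy; Section V.E requires both. The exposure is chiefly to the microbiological comparison and only partly to the clinical one.

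That both tests could be missed assumes only that some sites work from the chart. The direction and size of any bias in the treatment comparison would need assumptions about failures, withdrawals and site behaviour that the protocol does not supply, so no figure for bias or power is given. The matter goes beyond a clerical slip, because the chart's rule would lose efficacy assessments if followed. It is nevertheless a moderate consistency correction, not a defect that undermines the design.

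**What to change.** Reconcile Appendix I with Section V.E. In the Early Withdrawal column, replace X* with a plain X for Chest X-ray and for Culture & Gram stain, and restrict the existing footnote to the Visit #4 column. If the column is also meant to cover subjects who leave after Visit #3, give that case its own footnote.

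The cost is an edit to two cells and one footnote. No procedure is added, because Section V.E already requires both tests. The correction should reach sites before they use the chart, since a film or culture missed at withdrawal cannot be recovered.

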## APPENDIX II

### CENTRAL LABORATORY FNSTRUCTIONS

Pharmacokinetic samples will be shipped to:

Redi Lab  
Attn: Receiving Department  
[name]  
[name]

All pharmacokinetic samples must be processed according to the following guidelines. Draw blood into the provided purple top tube. Allow to clot for 30 minutes. Centrifuge for 10 minutes, pipette serum into small plastic container (provided) and IMMEDIATELY freeze. Ship the samples, on dry ice, for next day delivery using provided shipping boxes and containers.

Please fax the Pharmacokinetic requisition to Redi Lab on the day of shipment: [contact]

Any questions may be directed to the receiving department at Redi Lab: [contact].
